#### Swallowing Ratings:

Duplicate blinded ratings of the validated PAS, DIGEST, NZSS, and YRS will be performed by two experienced raters to index swallowing safety and efficiency (Tables 4-7). If a discrepancy occurs, a consensus meeting will be held with four experienced raters to finalize a rating.

**Table 4: The validated penetration-aspiration scale (PAS) scores and definitions used to index swallowing safety.**

Group:	PAS	Definition:
Non-Penetrator/Aspirator	1	Material does not enter the airway
	2	Material enters the airway, remains above the vocal folds, ejected from airway
Penetrator	3	Material enters the airway, remains above vocal folds, not ejected from airway
	4	Material enters the airway, contacts the vocal folds, and is ejected from airway
	5	Material enters the airway, contacts vocal folds, and is not ejected from airway
Aspirator	6	Material enters the airway, passes below vocal folds, ejected out of the airway
	7	Material enters the airway, passes below vocal folds, not ejected despite effort
	8	Material enters the airway, passes below vocal folds, no effort made to eject

**Table 5. The validated Dynamic Imaging Grade of Swallowing Toxicity (DIGEST) scale.**

Efficiency Grade and Definition	Safety Grade and Definition				
	0, PAS 1-2	1, PAS 3-4 any; 5-8 single or trace	2, PAS 5-6 intermittent or chronic, 7-8 intermittent/not gross	3, PAS 7-8 chronic and not gross or gross and not chronic	4, PAS 7-8 chronic and gross
0, <10% residue	0	1	2	3	3
1, 10-49% residue	1	1	2	3	3
2, 50-90% residue cracker	1	2	2	3	3

3, 50-90% residue pudding/liquid or >90% any	2	2	3	3	4
4, >90% residue all	3	3	3	4	4

**Table 6. The validated New Zealand Secretion Scale (NZSS) scores used to assess the location, amount, and response to secretions during FEES.**

Category	Score	Symptom
Location	0	Nil significant pooled secretions in pyriform fossae or laryngeal vestibule
	1	Secretions in pyriform fossae (above 20%)
	2	Secretions in laryngeal vestibule (beyond healthy lubrication of mucosa)
Amount in pyriform fossae	0	Nil significant pooled secretions in pyriform fossae (0–20%)
	1	Secretions in pyriform fossae, not yet full (20–80%)
	2	Secretions filling (80–100%) or over spilling pyriform fossae/interarytenoid space
Response	0	Secretions in pyriform fossae or laryngeal vestibule effectively cleared
	1	Ineffective attempts to clear or no response to secretions in pyriform fossae
	2	Ineffective attempts to clear secretions from laryngeal vestibule
	3	No response to secretions in laryngeal vestibule

**Table 7. The validated Yale Pharyngeal Residue Severity Rating Scale (YRS) scores used to assess the location, amount, and severity of residue.**

Vallecula Residue		
Score	Definition	Severity
I	No residue (0%)	None
II	Trace coating of the mucosa (1-5%)	Trace
III	Epiglottic ligament visible (5-25%)	Mild
IV	Epiglottic ligament covered (25-50%)	Moderate
V	Filled to epiglottic rim (>50%)	Severe

Pyriform Sinus Residue		
Score	Definition	Severity
I	No residue (0%)	None
II	Trace coating of the mucosa (1-5%)	Trace
III	Up wall to quarter full (5-25%)	Mild
IV	Up wall to half full (25-50%)	Moderate
V	Filled to aryepiglottic fold (>50%)	Severe

#### **Postoperative Research Evaluation 3:**

Following completion of the RST program and after cardiac surgery, patients will undergo a standardized FEES evaluation that will take approximately 30 minutes and health-related outcome measures will be tracked. For postoperative FEES examinations, the PI will ensure patient readiness and safety by completing a cognitive screen (Richmond Agitation-Sedation Scale score of 0) and by determining the patient's respiratory status is stable (SpO2 >90%, off CPAP/BiPAP for >30 minutes, respiratory rate <30 bpm). Table 8 shows a checklist for determining patient readiness for participating in a postoperative FEES.

Following confirmation that the participant is appropriate to proceed to swallowing testing, the research SLP will the same standardized FEES protocol as described in the preoperative research exams and will be performed at the participant's bedside. Postoperative FEES examinations will be performed within 72 hours of extubation with CS patients sitting upright in bed. During this period, the participant's vital signs will be monitored and although not

anticipated, testing will cease if a significant change is observed ( $\text{SpO}_2 < 90$ ,  $\text{BR} > 30$ , spike in blood pressure or overt signs of distress) or if the participant wishes to end testing early.

**Table 8: Checklist for determining patient readiness for postoperative FEES.**

Domain:	Criteria:
Alertness & Cognition:	
 
✓ Richmond Agitation- Sedation Scale of 0
 
✓ Oriented to time and place
 
✓ Alert and able to attend to conversation and follow commands
 

Stable Respiratory Status:	
 
✓ Able to remain off CPAP or BiPAP support for >30 minutes
 
✓ Demonstrates a respiratory rate <30
 

Physical Ability:	
 
✓ Ability to sit upright for testing
 

**Swallowing measures:** Two blinded judges will independently rate swallowing safety and efficiency using the validated penetration-aspiration scale (PAS), dynamic imaging grade of swallowing toxicity (DIGEST), the New Zealand secretion scale (NZSS), and the Yale pharyngeal residue severity rating scale (YRS). These scales are described in detail above in Tables 4-7.

**Health-related outcomes:** We will collect information on enrolled participants' medical history via the University of Florida Heart and Vascular hospital electronic medical records (Epic, Epic Systems Corporation, Verona, WI). Variables of interest may include previous history of dysphagia (y/n), previous cardiothoracic surgery (y/n), type of previous cardiothoracic surgery, previous cardiothoracic surgery notes, year of previous cardiothoracic surgery, dysphagia following previous cardiothoracic surgery (y/n), instrumental swallow evaluations after previous surgeries (y/n), primary surgery diagnosis, etc. Following surgery, enrolled participants will be closely monitored, and the following variables of interest will be tracked: time to oral diet, length of ICU and total hospital stay, intubation duration, extubation fast track status (y/n), pneumonia status, reintubation status, 30-day readmission status, and 90-day mortality status Epic. Given the nature of our therapy, additional metrics that provide insight into CS patients' pulmonary or swallow function may be extracted from respiratory therapists', speech-language pathologists, or other health care provider notes. These metrics may include things such as DLCO, respiratory rate, intubation duration, negative inspiratory force, instrumental swallow evaluation imaging (e.g., videofluoroscopy, FEES), etc. In addition to obtaining medical information from patients' charts, test results from research evaluations can be made available upon request to aid in medical care and reduce risk of repetitive testing.

**Aim 3 Outcomes** will include the postoperative PAS, DIGEST, NZSS, and YRS scores and the aforementioned health related outcomes of interest. We predict to see low rates of unsafe swallowing, and in those who do aspirate, we predict that they will demonstrate an adequate cough response to remove tracheal aspirate (PAS of 6). Further, we predict to observe low rates of pneumonia, reintubation, 30-day readmission, and 90-day mortality, as well as decreased time to oral intake and LOS for enrolled participants during their recovery.

**Sample size justification:** Given that this is a pilot study to determine primarily safety and feasibility data to determine whether a large-scale clinical trial is warranted, a justification based on statistical power to test hypotheses strictly at the  $\alpha=0.05$  level is not appropriate. The findings from this exploratory study will be used to perform future sample size and power calculations to examine the safety, feasibility, and impact of preoperative RST in a larger cohort of CS patients.

**Statistical analyses:** Descriptive statistics, magnitudes of estimates, and spaghetti and needle plots that visualize individual-level data across time points will first be utilized to summarize data in this small cohort and prior to performing conventional analyses and hypothesis testing.

**Aim 1:** Attendance, RST adherence, and adverse events will be summarized descriptively with frequency counts and percentages.

**Aim 2:** Descriptive statistics and an appropriate repeated measures analysis based on the distribution of data will be used to evaluate potential change in FVC, MEP, MIP, voluntary cough peak expiratory flow, and cough spirometry metrics, speech rate, number of pauses, duration of pauses, LCADL ratings across time points (pre-RST vs. post-RST).

**Aim 3:** Descriptive statistics will be used to summarize swallowing safety profiles postoperatively (frequency histogram, mean, mode, range of PAS, DIGEST, NZSS, YRS scores), and logistic regression will be used to compare swallowing safety and efficiency across timepoints. Postoperative rates of pneumonia, reintubation, duration of intubation, intubation fast track status, any related respiratory therapy outcomes, 30-day readmission, mortality, and time to oral intake/hospital LOS, etc. will be summarized descriptively (frequency counts, %) and compared to our historical data set in CS patients.

**Data Management and Quality Control:** Research Electronic Data Capture (REDCap) will be used to enter and store data for the current study, which is a secure web-based application hosted at the University of Florida. REDCap has a variety of features that streamline data entry and processing including the ability to download and export data directly to commonly used statistical analyses software. The ARC lab has successfully used REDCap for data collection, storage, and analyses for other research studies

**Table 9. Summary of Study Outcomes and analyses by specific aim.**

AIM:		STUDY VISIT	OUTCOMES:	ANALYSIS:
Aim 1	Feasibility & safety of RST	RST at-home program, Telehealth appts/In-person visit	# RST reps completed /# prescribed, # sessions completed /# scheduled, Adverse events.	Frequency counts, percentages.
Aim 2	Physiologic impact of RST	Research Exam 1, Research Exam 2	FVC, MEP, MIP, Cough PEF, Cough spirometry metrics, Speech rate, number of pauses, duration of pauses, LCADL ratings	Descriptive statistics, Repeated measures ANOVA (or non-parametric dep' distribution)
Aim 3	Postoperative health-related outcomes	Research Exam 3, 90-days postoperatively	Swallowing safety and efficiency, intubation duration, pneumonia, reintubation, 30-day readmission, 90-day mortality, time to oral intake, hospital LOS (ICU and total), relevant respiratory therapy outcomes	Frequency counts, Percentages, Logistic regression.

**Data Safety Monitoring Plan (DSMP):** [name] will provide medical oversight for this study and we will utilize standard IRB oversight to monitor any adverse events or protocol deviations. The UF-IRB will review the human subject protocol and will monitor the quality of research occurring under the approved protocol during annual continuing reviews. The IRB must approve the protocol annually, as the study progresses. Data safety monitoring will occur during weekly meetings to review Adverse Events (AE) and Protocol Deviation Logs with the PI and study team. In the event of an unanticipated adverse response, the participant's physician will be immediately notified, and the participant will be seen for a complete evaluation. Data, adverse events, and individual subject safety are monitored throughout each subject's evaluation as well as during weekly laboratory meetings with the PI and study team that adhere to the UF IRB regulations for reporting of AE's and protocol deviations.

**Potential Risks:** All participants will be required to pass a COVID-19 Test (i.e., COVID-19 negative) that is performed as standard of care in all surgical patients prior to being allowed to participate in this study. Thus, the risk for personal working on this project, in addition to potential cross contamination of equipment will not be a factor.

The following risks will be disclosed to all participants prior to obtaining their consent to participate:

- A Fiberoptic Endoscopic Evaluation of Swallowing (FEES) can result in discomfort, gagging or vomiting. Although extremely rare other complications that have been reported can include vasovagal episode (0.06%

reported incidence), laryngospasms (0.03% reported incidence), or epistaxis (0.3% reported incidence). The reported incidences of these adverse reactions to FEES are based on published reports in 6,000 patients.

- b) Aspiration (material in trachea) is always a possible risk during the FEES exam, as the test is intended to detect aspiration during swallowing.
- c) There are no documented complications of voluntary cough spirometry or pulmonary function testing.
- d) While RST has been safe and well-tolerated in a variety of patient populations, there is a chance it could result in dizziness, lightheadedness, fatigue, or shortness of breath.

**Potential Benefits:** Subjects may potentially benefit from participation through improved breathing, cough, and/or swallowing function. Participating in this study will also include an instrumental swallowing evaluation following surgery and may lead to the early identification of any swallowing impairments to minimize adverse effects of swallowing difficulty and to initiate preventative measures for risk of choking, respiratory difficulty and/or pneumonia post-operatively. Additionally, study participation may lead to sooner oral intake of food, liquids, and medications while in the hospital as a result of comprehensive swallowing testing being performed post-extubation.

**Conflict of Interest:** There is no conflict of interest to disclose for any study team member that is specifically relevant to this study.

**Summary and Conclusions:** This pilot study represents the first examination of the feasibility, safety, and physiologic impact of a targeted preoperative RST program in a small group of high-risk CS patients to prevent postoperative dysphagia and associated adverse outcomes. By carefully examining detailed aspects of physiology and health-related outcomes in a feasible design for this grant mechanism, the PI will collect high quality data to support her K99-R00 NIH grant application. These preliminary data will further inform future intervention paradigms in this challenging patient population where there is no current standard of care or evidence guided intervention guidelines for either pre or postoperative dysphagia management.

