## APPROACH:

**Overview:** The current *pilot* project seeks to determine the safety, feasibility, and impact of preoperative RST program in 25 CS patients who are at high risk for developing post-surgical dysphagia. Thus, this represents a 'proof of concept' study to support subsequent larger-scale clinical trials. Briefly, *Aim 1* will examine the feasibility and safety of the RST program by monitoring treatment adherence, telehealth/in-person session attendance, and closely monitoring adverse events related to RST. *Aim 2* will determine the physiologic impact of the RST program by comparing measurements of forced vital capacity (FVC), MEP, MIP, voluntary cough peak expiratory flow (PEF), and cough spirometry metrics as well as functional measures of dyspnea and (LCADL, Bamboo passage), before versus after RST (i.e., research exam 1 vs. research exam 2, Fig 3). Additionally, a FEES will be performed to index baseline swallowing and to provide secondary treatment outcomes indexed by the validated penetration-aspiration scale (PAS), dynamic imaging grade of swallowing toxicity (DIGEST), the New Zealand secretion scale (NZSS), and the Yale pharyngeal residue severity rating scale (YRS). Completion of Aims 1 and 2 will occur within one month prior to surgery (Fig. 3). *Aim 3* will involve monitoring and collection of health-related outcomes during the postoperative recovery phase and postoperative pulmonary function testing and FEES following extubation. This study timeline is depicted in Figure 3.

[figure not shown]

Fig. 3: Study Timeline.

**Design:** This study represents a *longitudinal pilot cohort study* intended to collect preliminary data regarding the safety and feasibility of a preoperative intervention program, to inform larger comparative studies that will utilize a between groups comparison. Similar study designs have been implemented in other pilot treatment studies in speech-language pathology. While study designs involving group comparisons were considered for this project, the current design was chosen to ensure feasibility and a tightly conducted pilot or proof of concept study to allow detailed and rigorous outcomes and analyses. Further, consideration was given to the nature, scope, budget, and timeline of this grant mechanism intended for new investigators, and it was determined that a smaller, feasible study was most appropriate.

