**Participants:** Twenty-five individuals undergoing cardiovascular surgery will be enrolled in this pilot project. Eligibility requirements are:

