#### **RST Program and Telehealth/In-Person Visits:**

**RST Program:** Enrolled CS patients will undergo a preoperative RST program immediately following Research Evaluation 1 (preoperative, pre-RST) with a targeted duration of 4-weeks that will vary dependent upon available time between the patients preop and surgery schedule. RST will be completed from the patients' home with portable expiratory and inspiratory training devices our lab has previously used: the EMST-150 or the EMST75 Lite and the IA-150 devices (Aspire Products, Gainesville, Florida, Fig. 4). The EMST 75 Lite has a resistance range of 0-75cm H2O and the EMST-150 and IA-150 devices have a resistance range of 30 to 150cm H2O and represent spring-loaded pressure threshold devices (Fig. 4). For completion of exercises, each device will be set to a patient's individualized 70% MEP or MIP. Following the baseline evaluation, trainers will be calibrated to the appropriate setting, and the patient will be trained on how to perform exercises. Additionally, they will be provided with a training manual that includes detailed instructions and photographs to provide reinforcement of the initial training session.

**Fig. 4: Respiratory training devices.** Images from <https://emst150.com/product/emst150-ia150-inspiratory-adapter-bundled-combo/> (Aspire Products, <https://emst150.com/>)

Participants will need to demonstrate proficiency in performing both the expiratory muscle strength training (EMST) and inspiratory muscle strength training (IMST) exercise prior to leaving the clinic and will be given a training log to record their daily sessions and a telehealth appointment card with weekly meeting dates and instructions for how to access the secure telehealth portal (a secure version of Zoom).

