In-Person Visit: CS patients will also have one in-person visit within participants’ homes or the research laboratory (DG-136) with a study team member at the mid-point of the RST program to ensure patients are using correct form and technique, to complete a safety and adverse event check, to answer any questions patients may have, and to assist with adherence issues. EMST/IMST devices will also be recalibrated by retesting MEP and MIP and setting the devices to 70%. LCADL ratings and functional speech measures (bamboo passage) will also be obtained.

Training Logs: CS patients will fill out daily training logs to track RST repetitions (adherence) and to note any adverse events related to RST. The PI will calculate the total number of repetitions completed by each participant at the conclusion of the training period.

Aim 1 Outcomes will include patient adherence to RST, attendance at telehealth/in-person treatment sessions, and adverse events associated with RST. We hypothesize that RST will be safe, well-tolerated, and feasible in CS patients as measured by high adherence to RST, attendance at all telehealth/in-person sessions, and no reported adverse events.

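### Aim 1 counts only RST-related adverse events and Aim 3 starts after surgery, so unplanned admission, a changed or cancelled operation, or death before surgery is a defined outcome under neither aim.

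*Combined protocol and SAP*

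**What the plan says.** The plan is for one cohort without a control group: "Twenty-five individuals undergoing cardiovascular surgery will be enrolled in this pilot project".

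**Aim 1.** The Overview under Approach describes "closely monitoring adverse events related to RST". The Aim 1 Outcomes paragraph lists adherence, "attendance at telehealth/in-person treatment sessions, and adverse events associated with RST". Table 9 gives the Aim 1 study visit as "RST at-home program, Telehealth appts/In-person visit"; Research Exam 2 is not listed there. The sources named are daily patient training logs (worded as RST-related events), one to five telehealth sessions a week and one mid-point visit. The checks at the telehealth sessions and the mid-point visit are not worded as RST-related only. The Aim 1 hypothesis is that no adverse events will be reported.

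**Aim 3.** The Health-related outcomes paragraph states: "Following surgery, enrolled participants will be closely monitored, and the following variables of interest will be tracked". Table 9 sets the Aim 3 window at Research Exam 3 and 90 days after surgery.

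**Training period.** The target is four weeks, but the duration "will vary dependent upon available time between the patients preop and surgery schedule".

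**Oversight.** The Data Safety Monitoring Plan (DSMP) describes monitoring during each participant's evaluation, weekly review of adverse event and protocol deviation logs, and notification of the participant's physician after an unanticipated adverse response.

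**The concern.** The Sample size justification presents the study as primarily one of safety and feasibility, meant to show whether a large trial is warranted. The participants are cardiac surgical patients training at home while they wait for an operation. The events that would weigh most in that decision are an unplanned admission, an operation moved or cancelled because the patient's condition changed, and death before surgery. The plan names none of these as an outcome.

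Two features make this more than a missing label. First, entry to the Aim 1 result depends on an event being tied to RST, yet the documents name no assessor and no procedure for that judgement. Second, most of the named sources need the patient to keep taking part. Someone who is admitted or dies stops filling in logs and attending sessions, and no chart check is prescribed for a patient who goes silent. Both features push the result towards the hypothesised absence of events, so RST could look safer than it was.

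**Working it through.** **Step 1: is there a stated figure to reproduce?** No. The plan gives no event rate, detectable rate or precision target for safety. On sample size it says that "a justification based on statistical power to test hypotheses strictly at the" 0.05 level is not appropriate. The check is therefore mainly a tracing of windows and definitions.

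**Step 2: trace each event between first RST session and surgery.**

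| Event | How the team might learn of it | Where the plan counts it |
|---|---|---|
| Unplanned admission or emergency visit | Log, telehealth check, mid-point visit, weekly log review | Aim 1 only if tied to RST. Not Aim 3: its 30-day readmission outcome is postoperative |
| Operation brought forward | Scheduling of Evaluation 2 or 3 | No outcome; a shorter programme |
| Operation postponed or cancelled | Scheduling of Evaluation 2 or 3 | No outcome; a changed programme length or a missing Evaluation 3 |
| Death before surgery | Missed sessions, scheduling | Aim 1 only if tied to RST. Not Aim 3: mortality is tracked after surgery |

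The middle column is not empty, so events can be noticed. The right-hand column has no all-cause entry in any row.

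**Step 3: the interval after the last session.** The list of procedures for Research Evaluation 2 covers lung function, speech, dyspnoea and FEES, with no adverse event check. The DSMP does cover evaluations in general terms. After Evaluation 2 no contact is scheduled until surgery. The documents do not give the length of that interval.

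**Step 4: what one uncounted event does to the safety result (illustration only).** Input: n = 25, from Participants. Intervals are exact (Clopper-Pearson), two-sided 95%.

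- 0/25: upper limit = 1 − 0.025^(1/25) = 13.7%.
- 1/25 = 4.0%: 0.1% to 20.4%.
- 2/25 = 8.0%: 1.0% to 26.0%.

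The documents do not say how a patient who never reaches surgery is counted. If one or two such patients were dropped, the report would read 0/24 (upper limit 14.2%) or 0/23 (14.8%), in place of 1/25 or 2/25.

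**Step 5: how likely is at least one such event?** The documents give no rate, so the rates p below are assumptions. P(at least one in 25) = 1 − (1 − p)^25.

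| Assumed p per patient | Expected events (25p) | P(at least one) |
|---|---|---|
| 1% | 0.25 | 22% |
| 2% | 0.5 | 40% |
| 5% | 1.25 | 72% |
| 10% | 2.5 | 93% |

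The range runs from unlikely to nearly certain. Step 2 does not depend on it.

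**The case against.** The best defence is that contact during training is close. Patients keep daily logs, have at least one telehealth session a week with a safety check, and are seen at mid-point. The DSMP adds monitoring at evaluations and weekly log review. The team must follow each surgery date, because Evaluation 2 comes before the operation and the postoperative FEES must fall within 72 hours of extubation. A death or a moved operation is unlikely to escape notice. The Aim 1 paragraph under Statistical analyses and the Table 9 outcome cell also say adverse events without the RST qualifier.

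Much of this stands, and it rules out stronger readings:

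- A reader might infer that safety data come only from training sessions. The daily logs and the DSMP contradict that.
- A reader might take the whole four weeks plus the wait for surgery as unobserved. The training weeks are the best-covered part. For patients who keep attending, the stretch without scheduled contact is the one after Evaluation 2, and nothing shows it to be long.
- A reader might conclude that patients who never reach surgery vanish. They would still appear in baseline, adherence and attendance data.

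What the defence does not supply is a rule that an event, once noticed, enters the safety result. The unqualified wording in the statistical section does not override the RST limit in the Overview and the Aim 1 Outcomes paragraph; at most it leaves the scope unclear. Log review cannot find what was never logged. The extra chart extraction allowed under Health-related outcomes is optional and concerns pulmonary and swallowing measures.

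**Conclusion.** The point holds as a gap in outcome definition and reporting. It does not show that events would go undetected. Followed as written, the plan could report no RST-related adverse events while a preoperative admission, a changed operation or a death stood in no outcome table. In 25 patients a single such event separates an estimate of 0% from one of 4%, with exact upper limits of 13.7% and 20.4%. Those figures show scale only, since whether any such event will occur rests on rates that the documents do not give.

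It would be wrong to infer that better capture would let this pilot rule out serious harm. Even a complete 0/25 leaves the true rate compatible with values up to 13.7%, and without a control group, preoperative events cannot be attributed to RST. The gain is a safety result with a stated window, scope and denominator. The change is worth making and does not affect the design.

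**What to change.** In the Aim 1 text and Table 9:

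1. Set the safety window from the first RST session to the start of surgery.
2. For every patient who starts RST, extract once from Epic, whatever the judged cause: unplanned admissions or emergency visits; the operation expedited, postponed or cancelled, with the reason; and death. Do this for patients who stop attending or never reach surgery as well.
3. Record relation to RST as a separate field that does not decide whether the event is counted, and say who makes the judgement.
4. Record adverse events at Evaluation 2 as part of Aim 1.
5. Report with all patients who started RST as the denominator, and state beside the Aim 3 rates how many did not reach surgery.

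The cost is a few REDCap fields and one look-up per patient in a record the team already uses. Treatment, visits and sample size stay as they are. The downside is that background cardiac events unrelated to RST will appear in the safety table; the report should say that they cannot be attributed to RST in a single-cohort design.
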